### 3 Analytical Methods

For nominal outcomes, parameter estimates will be calculated with 95% confidence intervals utilizing valid asymptomatic and/or exact binomial estimates. For continuous outcomes, measures of central tendency will be estimated based on the data distribution. Data following a Gaussian distribution (or data for which the central limit theorem appear applicable) will be summarized across study groups using a mean and standard deviation (and/or 95% confidence intervals). Continuous data which are not normally distributed (or for which the central limit theorem is not applicable) and ordinal data will be summarized across study groups using a median and interquartile range. Data transformations will be applied to approximate a Gaussian distribution as applicable. In particular, titers will be log-transformed prior to statistical comparisons and log10-transformed means (and standard deviations) and/or geometric mean titers will be estimated.

In general, between-cohort comparisons will be examined with nonparametric tests (Kruskal-Wallis for continuous data and Fisher's exact test for categorical data) unless assumptions are fulfilled for Analysis of Variance (ANOVA) or Pearson's  $\chi^2$ .

Importantly, this study is designed to enable estimates of clinical, immunological, and microbiological endpoints not to compare parameter estimates across study cohorts. Nonetheless, these comparisons across cohorts will be made and guided by an Omnibus null hypothesis as follows (where  $\theta$  is any nominal, continuous or ordinal parameter):  $\theta_{\text{Cohort A}} = \theta_{\text{Cohort B}} = \theta_{\text{Cohort C}} = \theta_{\text{Cohort D}}$

Post-hoc comparisons will include the following: Bonferonni, Sidak, Tukey's HSD or Newman-Keuls.

Additionally, nonparametric paired *t* tests (Wilcoxon paired signed rank test) may be used to compare continuous data at two separate time points unless assumptions are fulfilled for paired *t*-test. Additional

comparisons may include repeated measures analysis of variance with study group as the between subject factor and sample collection time-points as the repeated factor.

All statistical tests will be interpreted in a two-tailed fashion using an  $\alpha = 0.05$ .

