## 7 General Considerations

### 7.1 Analysis Population

#### 7.1.1 Safety Analyses

All AE's will be assessed for severity by the investigator. Essential in this assessment is the medical and clinical considerations of all information surrounding the event including any medical interventions required. Each event will be assigned one of the following categories: mild, moderate, severe, or life-threatening. The criteria below may be used for any symptom not included in the grading scale.

The eCRFs for AEs will reflect only the highest severity for continuous days and event occurred.

Mild	Grade 1	Does not interfere with routine activities; minimal level of discomfort
Moderate	Grade 2	Interferes with routine activities; moderate level of discomfort
Severe	Grade 3	Unable to perform routine activities; significant level of discomfort
Potentially life-threatening	Grade 4	Hospitalization or ER visit for potentially life-threatening event

FDA guidelines for toxicity will be followed; however if a subject is evaluated in an emergency room for nonlife threatening illness or symptoms (ie, visits emergency department on weekend for mild

problems because the physician's office is closed), the information from that visit will be reviewed and severity of the adverse event will be assessed according to the subject's clinical signs and symptoms.

As defined by the ICH guideline for GCP, the term "severe" is often used to describe intensity (severity) of a specific event (as in mild, moderate, or severe myocardial infarction); the event itself however, may be of relatively minor medical significance (such as severe headache). This is not the same as "serious," which is based on subject/event outcome or action criteria usually associated with events that post a threat to the subject's life or functioning. Seriousness (not severity) serves as a guide for defining regulatory obligations.

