The proportion of all subjects with each AE will be summarized with point estimate for percent and 95% confidence intervals calculated using valid asymptomatic and/or exact binomial estimates. Summary tables will be created which will describe the number and percentage of subjects who experience each adverse event. In addition, tables will be prepared to list each adverse event, the number of subjects experiencing an event at least once, and the proportion of subjects with adverse event(s). Adverse events will be divided into defined severity grades (mild, moderate, severe, or potentially life-threatening). The tables will also divide the adverse events by severity and related (definite, probable, possible) or unrelated (unlikely, not related) to the investigational product.

All subjects who receive vaccination will be included in the safety analysis. Adverse event data will be listed individually and summarized by body system and preferred terms within a body system for each treatment group. Serious and/or unexpected AEs will also be discussed on a case-by-case basis. For the tabulation of the AEs by body system, a subject will be counted only once in a given body system. For example, a subject reporting nausea and diarrhea will be reported as one subject, but the symptoms will be listed as two separate AEs within the class. Therefore the total number of AEs reported within a body system may exceed the number of subjects within the body system reporting AEs.

Rates of all adverse events will be analyzed by Pearson's Chi-square test (or Fisher's exact test if assumptions are not met for Pearson's Chi-square) to compare dose levels. Summary tables will be created which will indicate the number of subjects who experienced events. Vaccine-related events (probably or possibly related) will be tabulated by study group. In addition, tables will be prepared to list each adverse event, the number of subjects in each treatment group who experienced an event at least once, and the rate of subjects with adverse event(s). Adverse events will be divided into defined severity grades (mild, moderate, severe). The tables will also divide the adverse events by severity and relationship to the investigational product. All immunized subjects will be included in the safety analysis.

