### Results

**Table 3: Demographic characteristics of study subjects**

Characteristic	Participant (n =)	Screened (Not Enrolled)
Mean Age (sd)*	0	0
Age range	-	-
Gender (%)		
Male	0	0
Female	0	0
Race/Ethnicity		
African-American	0	0
Caucasian	0	0
Asian-American	0	0
Other	0	0

\*Measured in mean (standard deviation)

**Table 4:** Baseline characteristics of study participants (by cohort)

Cohort	A		B	C	D	E
	A-1	A-2				
Age a						
Gender [N (%)]						
Male						
Female						
Race/Ethnicity [N (%)]						
African-American						
White						
Asian						
Other						
LT IgA						
LT IgG						
CS6 IgA						
CS6 IgG						

a Presented as mean (standard deviation) or median (interquartile range)

**Table 5.** Safety profile of all adverse symptoms coded as ‘related’ to vaccine following vaccination [n(%)] (Groups compared using a Chi-squared analysis)

AE	Cohort A			Cohort B			Cohort C			Cohort D			Cohort E		
Dose	1	2	3	1	2	3	1	2	3	1	2	3	1	2	3
AE1															
AE2															
AE#															

**Table 6.** Safety profile of all adverse symptoms coded as ‘unrelated’ to vaccine following vaccination [n(%)] (Groups compared using a Chi-squared analysis)

AE	Cohort A			Cohort B			Cohort C			Cohort D			Cohort E		
Dose	1	2	3												
AE1															
AE2															
AE#															

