**A-1 (5 µg CssBA)**

**A-2 (100 ng dmLT)**

**B (5 µg CssBA + 100 ng dmLT)**

**C (5 µg CssBA + 500 ng dmLT)**

**D (15 µg CssBA + 100 or 500 ng dmLT)**

**E (45 µg CssBA +100 or 500 ng dmLT)**

**Vaccine Dose** (Circle one) **1 2 3**

**N =**

Cumulative summary of adverse signs and symptoms								
Symptoms	N (%) of volunteers exhibiting each adverse event							
	Grade 1		Grade 2		Grade 3		Grade 4	
	R	NR	R	NR	R	NR	R	NR
Local site pain								
Local site pruritis								
Vaccine site rash/eruption								
Vaccine Site Swelling (As reported by subject)								
Vaccine Site Tenderness								
Fever (subjective or objective)								
Headache								
Loose stools								
Arthralgia								
Myalgia								
Malaise								

R: Any sign or symptom coded as at least possibly related to the study product.

NR: Any sign or symptom coded as unrelated to the study product.

Note: The highest severity of an adverse event recorded for each subject (by relationship strata).

**COMBINED INTERIM SAFETY REPORT FOR 3-DOSE SERIES:  
Vaccine Cohort (Circle one)**

- A-1 (5 µg CssBA)**
- A-2 (100 ng dmLT)**
- B (5 µg CssBA + 100 ng dmLT)**
- C (5 µg CssBA + 500 ng dmLT)**
- D (15 µg CssBA + 100 or 500 ng dmLT)**
- E (45 µg CssBA +100 or 500 ng dmLT)**

N =

Cumulative summary of adverse signs and symptoms								
Symptoms	N (%) of volunteers exhibiting each adverse event							
	Grade 1		Grade 2		Grade 3		Grade 4	
	R	NR	R	NR	R	NR	R	NR
Local site pain								
Local site pruritis								
Vaccine site rash/eruption								
Vaccine Site Swelling (As reported by subject)								
Vaccine Site Tenderness								
Fever (subjective or objective)								
Headache								
Loose stools								
Arthralgia								
Myalgia								
Malaise								

R: Any sign or symptom coded as at least possibly related to the study product.

NR: Any sign or symptom coded as unrelated to the study product.

Note: The highest severity of an adverse event recorded for each subject (by relationship strata).

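### The only test the SAP names for comparing adverse events between dose groups ignores severity grade, so it can hardly respond to worsening reactions when nearly all subjects react

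*SAP*

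**What the plan says.** Safety is the only primary objective (SAP Section 4.1). Section 7.1.1 gives one method for comparing dose levels on adverse events: "Rates of all adverse events will be analyzed by Pearson's Chi-square test (or Fisher's exact test if assumptions are not met for Pearson's Chi-square". The same paragraph says what is counted, namely "the number of subjects in each treatment group who experienced an event at least once, and the rate of subjects with adverse event(s". That is a yes/no outcome per subject. The Table 5 shell in Section 9 attaches a test to the same kind of count, by cohort and dose and with no grade column: "Safety profile of all adverse symptoms coded as ‘related’ to vaccine following vaccination [n(%)] (Groups compared using a Chi-squared analysis". Table 6 does the same for unrelated events.

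Severity is recorded and reported. Section 7.1.1 states "Each event will be assigned one of the following categories: mild, moderate, severe, or life-threatening", and later "The tables will also divide the adverse events by severity and relationship to the investigational product". The interim report form in Section 10 already reduces each symptom to one grade per subject: "Note: The highest severity of an adverse event recorded for each subject (by relationship strata". No test is attached to any of these.

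Section 3 lets its omnibus hypothesis cover ordinal parameters, but the tests it names are "Kruskal-Wallis for continuous data and Fisher's exact test for categorical data", with ANOVA or Pearson's test if their assumptions hold. Ordinal data get no between-cohort test. Sections 3 and 6 both say that the study is not designed for comparisons between groups. Section 3 then says that such comparisons will be made, and sets a two-sided 0.05 level.

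**The concern.** A yes/no test uses only the boundary between no reaction and any reaction. If nearly everyone in every group reports a symptom, little can change at that boundary. A dose effect then shows mainly as a move from mild to moderate or severe, which the test cannot use. Local pain and tenderness are on the interim form's symptom list and could behave this way, although the SAP gives no expected rates.

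What is at stake is the final report. Section 4.2 includes finding a safe dose for a later challenge trial. A non-significant between-dose p-value beside graded tables that show worsening reactions could be read as evidence of no dose effect. A graded comparison added after the data are seen would be post hoc.

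**Working it through.** **Inputs from the SAP.** Groups B to E have 10 subjects each (Section 5, Table 2), the grades are 1 to 4 plus no event, and alpha is 0.05 two-sided. The SAP states no adverse event rate and no power. Its one sample-size figure, an interval for zero events in 8 subjects, does not bear on this point. All rates and shifts below are therefore assumptions.

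**Step 1: a worked table.** Assume 9 of 10 subjects react in each of B to E, with these highest grades:

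| Group | None | Mild | Moderate | Severe |
|---|---|---|---|---|
| B | 1 | 9 | 0 | 0 |
| C | 1 | 7 | 2 | 0 |
| D | 1 | 4 | 5 | 0 |
| E | 1 | 1 | 5 | 3 |

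- Any-grade test: every group has 9 with and 1 without, which equals the expected counts. Chi-square = 0, p = 1.
- Kruskal-Wallis on grade: the totals are 4, 21, 12 and 3, so the mid-ranks are 2.5, 15, 31.5 and 39. The rank sums are 137.5, 170.5, 220 and 292.
- Uncorrected H = 12/(40 × 41) × (137.5² + 170.5² + 220² + 292²)/10 − 3 × 41 = 9.908.
- Tie factor = 1 − (60 + 9240 + 1716 + 24)/(40³ − 40) = 1 − 11040/63960 = 0.827.
- H = 9.908/0.827 = 11.97 on 3 degrees of freedom, p = 0.0075.

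**Step 2: why the yes/no test saturates.** Take an 80% rate in Group B (odds 4) and odds ratios 1/2/4/8. The odds become 4, 8, 16 and 32, so the any-grade rates are 80%, 89%, 94% and 97%. Ten subjects per group can barely separate these.

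**Step 3: power by simulation.** Highest grade was scored 0 to 3, with a proportional-odds shift over B to E and permutation tests. Each cell gives the any-grade test versus Kruskal-Wallis on grade.

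| Any-grade rate in Group B | Odds ratios 1/2/4/8 | Odds ratios 1/1.5/2/3 |
|---|---|---|
| 20% | 40% vs 47% | 11% vs 12% |
| 30% | 39% vs 51% | 12% vs 12% |
| 50% | 34% vs 54% | 11% vs 16% |
| 80% | 9% vs 55% | 5% vs 17% |
| 90% | 3% vs 51% | 2% vs 17% |

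Repeat runs at 80% gave 9 to 11% versus 50 to 55% for the larger shift, and 5 to 7% versus 17% for the smaller.

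**Step 4: grade shifts but the reaction rate does not.** Here the moderate-or-worse share of reactors was set at 10%, 25%, 45% and 70% over B to E, with asymptotic tests.

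| Constant reaction rate | Any-grade chi-square | Kruskal-Wallis on grade | Rank trend on grade |
|---|---|---|---|
| 90% | 3% | 46% | 65% |
| 80% | 5% | 26% | 42% |
| 50% | 5% | 7% | 11% |

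The any-grade column is at its null level throughout. Kruskal-Wallis gains clearly at 80 to 90% but little at 50%, so a bare majority of reactors is not enough. Part of the trend test's advantage comes from using the dose order, not from using grade.

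**The case against.** The strongest reply is that nothing is hidden. The final tables split events by severity and relationship, and the interim form gives each cohort's counts at Grades 1 to 4. A reader might infer that the plan is blind to severity, or that escalation could go ahead on a misleading p-value. The SAP supports neither. Advancement rests on the SRC's review of graded safety data (Sections 5 and 10), and no stated decision uses the chi-square or Fisher result. This part of the reply stands.

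A reader might also infer that the SAP rules out a graded comparison. It does not. Section 3 admits ordinal parameters, Section 9 says that the shells may be modified, and the yes/no cut is read from the word rates and the shells. The accurate statement is that no graded test is specified.

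The size depends on the chosen inputs. With the smaller shift the gain is 0 to 5 points at rates up to 50%. Under a different large shift (log-odds rising from 0 to 2 over B to E), Kruskal-Wallis gained nothing at a 20% rate (40% vs 40%) and 12 points at 50% (34% vs 46%). Tables 5 and 6 are also split by dose and relatedness, whereas highest grade over the series makes a high reaction rate more likely. The simulations leave out Cohort A.

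Finally, the investigator assigns grade in an open-label trial, so a test on grade carries its own risk of bias.

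The disclaimer that the trial is not built for comparison does not answer the point. Section 3 says that the comparisons will be made, and a test that will be run should use the grade already collected where the rate carries little information.

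**Conclusion.** The point holds in limited form. The only between-dose test named for adverse events uses the rate of subjects affected and leaves grade out. For a symptom that nearly all subjects report, roughly 80 to 90% or more, it stays close to its null rejection rate while severity rises. At an 80% Group B rate the difference is about 9% versus 55% power with odds ratios 1/2/4/8, and about 5% versus 17% with 1/1.5/2/3. Both rest on assumed rates, a proportional-odds shift and 10 subjects in each of B to E. For uncommon events or modest shifts the gain is small.

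The shift is missed by one p-value, not by the safety analysis as a whole, and escalation is unaffected. The consequence is a possible mismatch in the final report between that p-value and the severity tables. The change is cheap and worth making before analysis.

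**What to change.** In Section 7.1.1:

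- Keep n(%) with exact intervals, and keep Fisher's exact test for uncommon or unsolicited events.
- For each solicited symptom, add one prespecified exact rank comparison of the subject's highest grade, scored 0 (none) to 4, across groups. Choose either Kruskal-Wallis or an ordered trend test now, not after the data are seen.
- If a trend test is chosen, state the group order. Table 2 allows D and E to revert to 100 ng dmLT, in which case the move from C to D raises CssBA but lowers dmLT. The two arms of Cohort A do not fit a single order either.
- Label the comparison descriptive, in line with Sections 3 and 6. The interim form lists 11 symptoms, so 11 × 0.05 = 0.55 nominally significant results would be expected if no symptom differed between groups.

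In Section 9, show n(%) by grade in Tables 5 and 6 and replace the caption note "Groups compared using a Chi-squared analysis" with the tests actually used.

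The cost is SAP wording and two table shells. No new data are needed, and SAS, which the SAP already names, runs the exact Kruskal-Wallis test. The drawbacks are little gain for rare events, no single rate difference from a rank test (so the n(%) columns must stay), and reliance on investigator-assigned grades without blinding.

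### SAP Section 7.1.1 gives two definitions of a vaccine-related AE and two severity scales; read literally, the by-group version omits definitely related events and has no Grade 4 level

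*SAP*

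**What the plan says.** Section 7.1.1 of the SAP describes the AE tables twice.

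- **Definition paragraph** (it opens with the proportion of subjects having each AE). On severity: "Adverse events will be divided into defined severity grades (mild, moderate, severe, or potentially life-threatening". On relationship: "The tables will also divide the adverse events by severity and related (definite, probable, possible) or unrelated (unlikely, not related) to the investigational product".
- **By-group paragraph** (the last of the section; it opens with the dose-level test). On relationship: "Vaccine-related events (probably or possibly related) will be tabulated by study group". On severity: "Adverse events will be divided into defined severity grades (mild, moderate, severe", and the list closes there. A further sentence says the tables are split by severity and by relationship to the product, without saying which codes count as related.

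Three other places bear on the point.

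- The grading text at the start of Section 7.1.1 sets four levels: "Each event will be assigned one of the following categories: mild, moderate, severe, or life-threatening".
- The interim report forms in Section 10 have columns for Grades 1 to 4 and this key: "R: Any sign or symptom coded as at least possibly related to the study product".
- In Section 9, the titles of Tables 5 and 6 divide AEs by cohort into those coded related and those coded unrelated, with no severity split and no list of codes.

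**The concern.** Safety is the only primary objective (Section 4.1), and the related-AE rate by group is one of the main descriptive results that serve it. The by-group paragraph is the one that says how related events are tabulated by study group, and its bracket names two of the three related codes. An event coded definite is then outside the vaccine-related tabulation, yet it is not unrelated either, because the SAP's unrelated codes are unlikely and not related. The same paragraph's severity list stops one grade short of the scale on which every event is graded.

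Any resulting error in the related-AE rate has one direction: the rate is understated, and the missing events are those most firmly attributed to the product. A reader comparing the SRC report with the final by-group table could find different related-AE counts for the same cohort, with nothing in the SAP to explain the gap.

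**Working it through.** No figure in the SAP depends on this point, so there is none to reproduce. The check is a comparison of the texts, followed by the size of one omitted subject.

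**Step 1. Set the rules side by side.**

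| Place in SAP | Codes counted as related | Severity levels |
|---|---|---|
| 7.1.1, grading text and scale | not addressed | 4 |
| 7.1.1, definition paragraph | definite, probable, possible | 4 |
| 7.1.1, by-group paragraph | probable, possible | 3 |
| 9, Tables 5 and 6 | coded related / unrelated, codes not listed | none |
| 10, interim report forms | possible or stronger | 4 |

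The by-group paragraph is the outlier on both counts. It omits one of three related codes and one of four grades. The SAP gives no reason for a narrower definition and does not label it a sensitivity analysis.

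**Step 2. Trace what each omission touches.**

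- *Relationship.* The bracket qualifies the by-group tabulation of vaccine-related events and nothing else.
- *Severity.* The three-grade list is a separate sentence about AEs in general. It is not part of the definition of the vaccine-related table and does not say which events are counted. It leaves a Grade 4 event without a level in that split.
- *Dose-level test.* The paragraph opens with "Rates of all adverse events will be analyzed by Pearson's Chi-square test". The test has no filter on relationship or grade, so its numerator is the same under either rule.

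**Step 3. Size of one omitted subject.** Table 2 in Section 5 gives 5 subjects in each half of Group A and 10 in each of Groups B to E. A subject drops out of a row if all of that subject's related events in that row are coded definite. The change in the rate is 1/n:

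- n = 5: 1/5 = 20 percentage points
- n = 10: 1/10 = 10 percentage points

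**Step 4. Effect on the reported interval.** The event counts here are assumptions for illustration. The exact (Clopper-Pearson) 95% limits for x events in n subjects are the 0.025 quantile of Beta(x, n − x + 1) and the 0.975 quantile of Beta(x + 1, n − x). For x = 0 the lower limit is 0 and the upper limit is 1 − 0.025^(1/n), which for n = 10 is 30.8%.

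| Assumed events in a group of 10 | Definite counted | Definite not counted |
|---|---|---|
| 1 related, and it is definite | 1/10 = 10% (0.3% to 44.5%) | 0/10 = 0% (0% to 30.8%) |
| 3 related, of which 1 definite | 3/10 = 30% (6.7% to 65.2%) | 2/10 = 20% (2.5% to 55.6%) |

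The SAP does not say what share of related events would be coded definite, so the undercount in a given row can be anything from none to all of the related subjects. Five of the eleven symptoms on the Section 10 forms concern the injection site. If such reactions are often coded definite, which is an assumption, the omitted category would not be empty.

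**The case against.** The strongest reply is that the by-group paragraph largely repeats the definition paragraph and was simply not harmonised with it, so a sensible programmer would use the full definition. Much of this stands. Table 5 is titled for all events coded related, and the only full list of related codes in the SAP includes definite. The SRC report, on which advancement between groups rests, counts everything possible or stronger and has a Grade 4 column.

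A reader might infer more than the document supports, in two ways.

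- *That definitely related and Grade 4 events drop out of the primary safety comparison.* They do not. The dose-level test is on all AEs. The SAP names no single primary safety comparison, and Section 6 says the study is not designed to show significant differences between groups.
- *That Grade 4 events are lost.* They are not. They remain in the individual listings, the overall AE rates, the four-grade tables of the definition paragraph, Table 5 or 6, and the SRC report. Serious or unexpected events are also discussed one by one.

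The reply does not remove the contradiction. Table 5 does not define related, and Section 9 calls the tables samples that may be changed. The sentence with the narrow bracket describes the same kind of by-group table. Two programmers could apply different rules and each cite Section 7.1.1. Table 5 also carries a chi-squared comparison of groups, so if the narrow rule were used there, the counts entering that comparison would change too.

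**Conclusion.** The point holds as an internal contradiction in Section 7.1.1. Read literally, the by-group tabulation of vaccine-related AEs omits events coded definite, and the by-group severity split has no Grade 4 level. Both differ from the section's own definition paragraph, and both could put the final tables at odds with the SRC report.

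Each subject omitted lowers a related-AE rate by 10 percentage points in a group of 10 and by 20 in a sub-group of 5. The total effect cannot be stated, because it depends on how many subjects have only definite related events and on which sentence the programmer follows. If the fuller definition is used throughout, nothing is miscounted. The dose-level test on all AEs, the listings, the four-grade tables and the SRC escalation report are unaffected under either reading.

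**What to change.** In the last paragraph of Section 7.1.1:

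1. Change the bracket on vaccine-related events to read *definitely, probably or possibly related*.
2. Add the fourth grade, *potentially life-threatening*, to the three severity levels listed.
3. Add one sentence stating that this definition of related, with unrelated meaning unlikely or not related, applies to all by-group tables, including Tables 5 and 6, and matches the key of the SRC report.

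The cost is two wording corrections and one added sentence. No data, test, population or SRC form changes. The change should be made before the final tables are programmed.
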